#### 5.9.3 Loss to follow-up

A study participant will be considered as lost to follow-up if he/she repeatedly fails to return for scheduled visits and cannot be contacted by the site.

The site must take preventive measures to avoid a study participant being lost to follow-up (e.g., document different ways of contact such as telephone number, home address, email address, person to be contacted if the study participant cannot be reached).

The following actions must be taken if a participant fails to return to the site for a scheduled study visit:

- The site staff must attempt to contact the study participant and reschedule the missed visit as soon as possible and counsel the study participant on the importance of maintaining the assigned visit schedule and ascertain if the study participant wishes to and/or should continue in the study.
- If the study participant cannot be reached, the site must make a reasonable effort to contact the study participant and document all attempts in the study participant medical chart. Reasonable efforts include, where possible, three telephone calls to the last available telephone number and one registered/certified letter to the study participant's last known mailing address or local equivalent methods.
- If the study participant is still unreachable after all contact attempts listed above, he/she will be considered to be lost to follow-up.

The date of last contact with the study participant will be collected in the eCRF.

# **6 TREATMENTS**

#### 6.1 Study treatment

#### 6.1.1 Investigational treatment and matching placebo description

ACT-539313 is supplied by the sponsor as capsules at a strength of 100 mg. Matching placebo will be supplied by the sponsor as identical capsules indistinguishable from ACT-539313.

#### 6.1.2 Study treatment dosing and administration

ACT-539313 or matching placebo will be available as capsules at a strength of 100 mg, taken orally, b.i.d. in the morning at breakfast and in the evening at dinner with a glass of water (approx. 240 mL / 8 fl. oz.), during the treatment period.

On study visit days when blood samples will be collected, participants will be asked not to take their morning dose until blood samples are drawn.

#### 6.1.2.1 Study treatment dose adjustments

Study treatment dose adjustments are not permitted.

#### 6.1.3 Treatment assignment

A total of approximately 120 study participants will be randomized in a 1:1 ratio to ACT-539313 or placebo. Randomization will not be stratified.

After verifying that the study participant meets all inclusion criteria and none of the exclusion criteria, the investigator/delegate contacts the IRT system at Visit 2 to randomize the study participant. The IRT assigns a randomization number to the study participant and assigns the treatment kit number, which matches the treatment arm assigned by the randomization list to the randomization number.

The IRT system is handled by an external independent vendor who will generate the randomization list.

#### 6.1.4 Blinding

This study will be performed in a DB fashion. The investigator, site study personnel, the study participants, CRAs, sponsor personnel, and vendor/CRO personnel responsible of the conduct of the study, will remain blinded to the study treatment allocation until study database lock.

To ensure adequate supply of study treatment, the IRT vendor personnel responsible for clinical study distribution and the sponsor individuals contributing to clinical supply distribution will need to be unblinded at study participant level and depot level, respectively. These persons will be clearly identified, their unblinding status will be documented in the trial master file and controlled as per sponsor/CRO procedures.

Until the time of unblinding for final data analysis, the randomization list is kept strictly confidential, and accessible only to IRT vendor and authorized persons (i.e. dedicated members of the Pharmaceutical Development group), who are not involved in the conduct of the study.

The investigational treatment and its matching placebo are indistinguishable, and all treatment kits will be packaged in the same way.

To minimize the possibility of systematic unblinding, the results of the PK data will not be communicated to the investigator, study personnel, study participants, CRAs, any sponsor or vendor/CRO personnel involved in the conduct of the study. Results will be transferred by the sponsor Bioanalytical Laboratory group (for PK data) to the sponsor and CRO personnel involved in the conduct of the study only after database lock.

# 6.1.5 Unblinding

# 6.1.5.1 Unblinding for final analyses

Full randomization information will be made available for data analysis only after database lock, in accordance with the sponsor and/or the CRO's Quality System documents.

# 6.1.5.2 Unblinding for Independent Data Monitoring Committee or interim analyses Not applicable.

# 6.1.5.3 Unblinding for suspected unexpected serious adverse reactions

If a SUSAR [see definition in Section 8.2.3] occurs for a study participant, sponsor's Global Drug Safety will perform unblinding of the treatment assignment for that study participant in order to meet regulatory reporting requirements.

Unblinded information will be accessible only to sponsor personnel who need to be involved in the safety reporting to the regulatory authorities and/or IECs/IRBs.

# 6.1.5.4 Emergency procedure for unblinding

The identity of the study treatment may be revealed only if the study participant experiences a medical event, the management of which would require knowledge of the blinded treatment assignment. In this case, the investigator/delegate can receive the unblinded treatment assignment through the IRT.

In these situations, the decision to unblind resides solely with the investigator and must be clearly justified and explained. Whenever it is possible, and if it does not interfere with (or does not delay) any decision in the best interest of the study participant, the investigator is

invited to discuss the intended unblinding with the sponsor personnel. The occurrence of any emergency unblinding during the study must be clearly justified and explained by the investigator. In all cases, the sponsor personnel must be informed as soon as possible before or after the unblinding.

Once unblinding has occurred, the knowledge of the blinded treatment assignment must stay restricted at the site level.

A study participant may stay on study treatment after unblinding provided the investigator considers it is in the participant's best interest.

The circumstances leading to unblinding must be documented in the hospital charts, the ISF, and in the IRT system.

#### 6.1.6 Study treatment handling/preparation/storage/accountability

Manufacture, labeling, packaging, and supply of study treatment will be conducted according to Good Manufacturing Practice, GCP, and any local or national regulatory requirements.

All study treatment supplies are to be used only in accordance with this protocol, and not for any other purpose.

#### 6.1.6.1 Study treatment packaging and labeling

Study treatment is provided as capsules and supplied in childproof bottles.

Study treatment is labeled to comply with the applicable laws and regulations of the countries in which the study sites are located.

#### 6.1.6.2 Study treatment distribution and storage at the site

Study treatment supplies must be kept in an appropriate, secure area and stored according to the conditions specified on the label and in the IB and/or Investigational Medicinal Product handling manual [ACT-539313 IB].

#### 6.1.6.3 Study treatment dispensing

The study participants will receive sufficient study treatment to cover the period up to the next scheduled visit. Study participants are asked to return all used, partially used, and unused study treatment bottles at each visit. Should the treatment bottle dispensed at a scheduled visit be lost or damaged, a replacement bottle can be requested via the IRT system. In exceptional circumstances (e.g., pharmacist not available on the date of the scheduled visit), the investigator/delegate may contact the IRT system shortly prior to the scheduled visit (with the exception of the randomization visit [see Section 6.1.3] to obtain the treatment kit number(s) to be dispensed at the visit.

The protocol-mandated study treatment dispensing procedures may not be altered without prior written approval from the sponsor. In exceptional circumstances (e.g., if the study participant lost the study treatment between two visits, or if the study participant is unable to return to the site due to a medical emergency / hospitalization at another hospital / long travel distance), unscheduled dispensing and delivery of study treatment may occur outside of a scheduled visit. If the study treatment needs to be shipped to the study participant, the site staff must first contact the sponsor representative to check whether the dispensing and delivery process is in accordance with the sponsor/CRO's Quality System documents as well as any local or national regulatory requirements.

An accurate record of the date and amount of study treatment dispensed to each study participant must be available for inspection at any time.

Study participant will be dispensed new bottle(s) at each visit. Study drug from the newly received bottle is always to be taken in the evening at home.

The morning dose will be taken at home from the current bottle, except for Visit 5 (Week 4), Visit 7 (Week 8) and EOT visit where the morning dose will be withheld until the participant is on site and will be taken after PK laboratory samples are drawn.

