### Table 1Schedule of activities

PERIODS	Name	SCREENING		TREATMENT							FOLLOW-UP	UNSCHEDULED
	Duration	2–4 weeks		12 weeks							7–13 days	NA
VISITS	Number	1	2	3	4	5	6	7	8	ЕОТ	EOS	U1
	Name	Screening	Randomization	Week 1	Week 2	Week 4	Week 6	Week 8	Week 10	Week 12 / End-of-Treatment 	End-of-Study visit	Unscheduled visit 
	Time window	Day –28 to Day –1	Day 1	Day 8 (±1)	Day 15 (±2)	Day 29 (±2)	Day 43 (±2)	Day 57 (±2)	Day 71 (±2)	Day 85 (±2) or 1 to 5 days after last dose if premature EOT	10 ± 3 days after EOT	Any day between ICF signature and EOS
Signature of I form	nformed consent	Х										
Eligibility		Х	Х									
Demographics	5	Х										
Medical histor	ry	Х										
Previous/conc	omitant therapy	Х	Х	Х	Х	Х	Х	Х	Х	Х		
Physical exam	ination	Х								Х		
Body weight a	nd height 	Х	Х	Х	Х	Х	Х	Х	Х	Х		
Vital signs (Bl	P, PR, RR, T°)	Х	Х	Х	Х	Х	Х	Х	Х	Х		(X) 
12-lead ECG (	(central)	Х								Х		(X) 
Hematology /	blood chemistry 	Х				Х		Х		Х		(X) 
Serum/urine p	oregnancy test 	Х	Х			Х		Х		Х	Х	(X) 
Thyroid funct	ion	Х										
Urine drug sc	reen	Х	Х	Х	Х	Х	Х	Х	Х	Х		
Viral serology	τ	Х										
PK sampling 						Х		Х		X		
Binge eating d	liary completion									•••••		
Stanford Slee	piness Scale 			 	 ▶							
Binge eating d	liary check		Х	X	X	X	X	X	X	Х		
YBOCS-BE			Х			X		X		Х		
PGI-S			Х			X		X		Х		

Doc No D-21.148

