5.4.2 Compliance with study treatment

Study treatment compliance will be assessed through study treatment dispensing and accountability.

The following formula will be used to calculate compliance for the treatment period:

Study treatment compliance (%) = [(number of capsules dispensed – number of capsules returned^{*}) / (treatment duration – total duration of treatment interruptions)] $\times 0.5^{**} \times 100$

* If a study participant did not return his/her bottle (e.g., it is lost), compliance will not be calculated, and the compliance will be set to missing.

** To account for 2 capsules taken per day (i.e., b.i.d.).

Treatment duration and total duration of treatment interruptions are calculated using the dedicated eCRF page 'Study Treatment Log' as follows:

- Treatment duration (days) = date of last drug intake of study treatment date of first drug intake of study treatment + 1 day.
- Total duration of treatment interruptions (days) is the sum of all the treatment interruptions' durations. A treatment interruption duration = date restarted study treatment end date of study treatment due to an interruption. For example, if a study participant stopped his/her treatment on 19MAR2021 and started again on 23MAR2021, as the treatment is taken on the start and end dates, the calculation will be 23MAR2021 19MAR2021 = 4 days of interruption. Should the study participant interrupt the treatment again for 7 days, the total duration of interruptions will be 11 days. Moreover, if a study participant misses one dose, either the evening or the morning dose, a treatment interruption of 1 day will be counted.

Study treatment compliance (including categories 0%, > 0% – < 50%, 50% – < 70%, 70% – < 80%, 80% – < 90%, 90% – < 100%, 100%, > 100%), treatment interruptions (Yes/No), and duration of treatment interruptions will be summarized.

The number (%) of study participants who have treatment interruptions, and the corresponding reasons will be tabulated.

Study treatment compliance, dispensing and accountability data will be listed.

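### The compliance formula in SAP 5.4.2 counts the half-dosed first and last treatment days as full days, so a completer with no logged interruption who takes every capsule scores 98.8%, not 100%

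*Protocol*

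**What the plan says.** - **First day.** Protocol 6.1.6.3 has new bottles dispensed at each visit and says "Study drug from the newly received bottle is always to be taken in the evening at home". The Schedule of activities (Protocol Table 1) puts the first dispensing at Visit 2, Day 1, so the first intake is that evening. SAP 11.7 fits this: it analyses sleepiness on study days 2 to 15 because no such data should exist for the day of randomization.
- **Last day, completers.** The same protocol section has the morning dose taken at home except at Visit 5, Visit 7 and the "EOT visit where the morning dose will be withheld until the participant is on site and will be taken after PK laboratory samples are drawn". Bottles are returned at each visit, and Protocol 7.1 ends the treatment period on the day of the last dose. No evening dose is foreseen after EOT.
- **Last day, early stoppers.** Table 1 times the EOT visit as "Day 85 (±2) or 1 to 5 days after last dose if premature EOT". Their last capsule may be a morning or an evening one.
- **Formula.** SAP 5.4.2 takes capsules dispensed minus returned, divides by treatment duration minus interruption days, and multiplies by 0.5 and 100. Duration is the date of last intake minus the "date of first drug intake of study treatment + 1 day". The factor 0.5 is footnoted "To account for 2 capsules taken per day (i.e., b.i.d".
- **Interruptions.** In the same section an interruption is the restart date minus the stop date with no added day, on the ground that treatment is taken on both dates. One missed dose, morning or evening, counts as a 1-day interruption.
- **Use.** SAP 5.4.2 tabulates compliance with separate categories for 90% to below 100%, exactly 100%, and above 100%. SAP 4.1.4 requires at least 80% for the per-protocol set (PPS) and, as a separate criterion, no premature treatment discontinuation.

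**The concern.** The numerator is a true capsule count. The denominator assumes two capsules on every calendar day from first to last intake, although the dosing rules give one on the first day and, for completers, one on the last. The ratio is therefore below 100% for a participant who has missed nothing and has no logged interruption. The interruption rule in the same denominator does net the two half days, so one formula follows two conventions.

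What is at stake is whether the compliance table means what its labels say. The 100% category would hold no fully adherent completer without a logged interruption, small over-use would not appear above 100%, and a few very early stoppers would be shown as poor compliers without having missed a dose.

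**Working it through.** **The plan's own example.** Stop on 19 March 2021 and restart on 23 March 2021: 23 − 19 = 4 days; with a further 7 days, 11. Both reproduce. Four days is 8 capsules. That matches a stop after the morning dose and a restart with the evening dose (1 + 2 × 3 + 1 = 8), so this rule treats each end as a half day. The SAP gives no expected score for a perfect taker.

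**Inputs.** Evening-only first day and morning-only EOT day (Protocol 6.1.6.3); EOT on Day 83 to 87 (Protocol Table 1); duration and factor 0.5 (SAP 5.4.2). L is the day of last intake, with first intake on Day 1.

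**Perfect intake, no logged interruption.**
- Morning last dose: capsules = 1 + 2(L − 2) + 1 = 2L − 2.
- Evening last dose: capsules = 2L − 1.
- SAP score = capsules / L × 0.5 × 100.

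**Completers.** L = 85: 1 + 2 × 83 + 1 = 168 capsules, which is exactly 12 weeks twice daily (84 × 2). Score = 168/85 × 50 = 98.82%. L = 83: 164/83 × 50 = 98.80%. L = 87: 172/87 × 50 = 98.85%. If an evening dose did follow on Day 85, 169/85 × 50 = 99.4%, still not 100%.

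**Extra capsules, L = 85.** One extra: 169/85 × 50 = 99.4%. Two extra: 170/85 × 50 = 100.0%. Neither is above 100%.

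**Early stoppers, every scheduled dose taken.**

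| Last intake | Morning last dose | Evening last dose |
|---|---|---|
| Day 1 | not possible | 50.0% |
| Day 2 | 50.0% | 75.0% |
| Day 3 | 66.7% | 83.3% |
| Day 4 | 75.0% | 87.5% |
| Day 5 | 80.0% | 90.0% |
| Day 8 | 87.5% | 93.8% |
| Day 15 | 93.3% | 96.7% |

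**PPS cut-off, completer at Day 85, no logged interruption.** The SAP formula needs 0.80 × 170 = 136 capsules; a scheduled-dose denominator needs 0.80 × 168 = 134.4, so 135. Only a count of exactly 135 changes side: 135/85 × 50 = 79.4% against 135/168 = 80.4%.

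**Interaction with the single-missed-dose rule, L = 85.** Each missed capsule removes two expected ones.
- One missed: 167/84 × 50 = 99.4%, which happens to equal the true 167/168.
- Two missed on different days: 166/83 × 50 = 100.0%.
- Three missed on different days: 165/82 × 50 = 100.6%, above the perfect taker's 98.8%.

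**Could the half days be logged as interruptions?** That gives 168/(85 − 2) × 50 = 101.2%, so it does not restore 100% either.

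**The case against.** The strongest reply is that nothing inferential depends on this. Outside its own summary and listing, compliance is used only for the PPS threshold. Perfect completers clear it easily, early stoppers are excluded by their own criterion, and the 1.2-point shortfall for completers is the same in both arms. That stands, apart from the single borderline count shown in the working.

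Extra intake also has its own route: Protocol 8.1.7 requires a mismatch to be reviewed, recorded as an AE if consistent with medication error or overdose, and the number of extra capsules to be entered in the eCRF. The compliance category is not the overdose detector. That stands too.

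A reader might infer that an arm with more early discontinuations, for example for somnolence, would look markedly less adherent. The documents do not support this. Scores of 50% to 75% need a stop by Day 4 with a morning last dose, or by Day 2 with an evening one, and neither document gives a count of such stops. The table would also be read beside treatment duration by category and the Kaplan-Meier plots of time to discontinuation (SAP 5.4.1), and discontinuation reasons by arm (SAP 5.1.3).

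What the reply does not remove is that the SAP's 100% category is out of reach for a fully adherent completer with no logged interruption.

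**Conclusion.** The point holds as a minor definitional error in SAP 5.4.2. Its size is 98.80% to 98.85% in place of 100% for perfect completers, and 50% to 75% in place of 100% for the very early stops described. The primary analysis on the FAS is untouched. A reader might take the low early-stop scores as evidence that the PPS is distorted. It is not: those participants are out under the discontinuation criterion whatever they score, and among completers only a borderline count could move.

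The result assumes that the first intake is the evening of Visit 2, as the dispensing rule implies, that completers take no capsule after the EOT morning dose, and that no interruption is logged. If only the first day is a half day, the completer's score is 99.4% and the conclusion is the same.

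**What to change.** In SAP 5.4.2 define compliance as capsules taken divided by capsules scheduled between first and last intake, times 100. Count scheduled capsules with one half-day convention for both duration and interruptions: 1 on the evening-only first day, 1 on the last day if the last intake is a morning dose (so by rule for completers), and 2 on other days. A perfect Day 85 completer then scores 168/168 = 100%.

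Change the single-missed-dose rule at the same time, so that one missed dose no longer removes a full day. Merely subtracting two capsules from the present denominator would score a Day 85 completer who missed one dose at 167/(2 × 84 − 2) = 167/166 = 100.6%. Under the full definition this participant scores 167/168 = 99.4%.

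State how morning or evening is assigned for early stoppers. SAP 11.1 takes only the date of last intake from the Study Treatment Log. The dosing time in Protocol 7.2.6 is for the dose before the blood draw. For completers that precedes the final EOT capsule; using it would class them as evening-last and give 168/169 = 99.4%. For early stoppers it can help where the EOT sample was drawn; otherwise a stated assumption is needed, with one capsule at stake.

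The cost is a short edit to SAP 5.4.2 and its program. Dosing does not change, and completers need no new data.

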# 6.1.6.4 Study treatment accountability

The inventory of study treatment dispensed to and returned by the study participant (i.e., study treatment accountability) must be performed by site personnel on the day of the visit and before dispensing further study treatment. The inventory is to be recorded by site personnel in the site documentation and in the eCRF. The study treatment accountability log in the eCRF will include at least the following information for each study treatment unit dispensed to the study participant:

- Number of bottles dispensed
- Dispensed bottle ID number
- Date dispensed / number of capsules dispensed
- Date returned / number of capsules returned

All study treatment supplies, including partially used or empty bottles must be retained at the site until verified by the CRA.

If the study participant forgets to bring the remaining study treatment to a study visit, he/she must be instructed to not take any capsules from the remaining study treatment bottle and to return it at the next visit.

ACT-539313		
Binge Eating Disorder		
Protocol ID-082A201	Confidential	
Final Version 3		
4 May 2021, page 59/140		

#### 6.1.6.5 Study treatment return and destruction

The protocol-mandated study treatment returning procedures may not be altered without prior written approval from the sponsor. On an ongoing basis and/or on termination of the study, the CRA will collect used and unused treatment kits, which will be sent to the warehouse, where the sponsor/depot personnel or a deputy will check treatment reconciliation.

In certain circumstances (e.g., local hospital procedures), used and unused study treatment containers may be destroyed at the site. In general, this can only be done once study treatment accountability is finalized and has been checked by the sponsor personnel representative and written permission for destruction has been obtained from the sponsor. Exception might happen in case a local process requests immediate destruction of the study treatment. Such local study treatment destruction processes must be provided and approved by the sponsor in advance.

# 6.1.7 Study treatment compliance

The investigator/delegate must discuss the non-compliance with the study participant to clarify the reasons and to take appropriate actions to avoid re-occurrence. This discussion and its outcome must be documented in the source documents.

